12.5.2.3 Sensitivity Analyses

There are no planned sensitivity analyses of the primary endpoint.

12.5.3 Key Secondary Estimands

The secondary estimand attributes are given in Section 9.1.2.

12.5.3.1 Progression Free Survival (PFS)

The key secondary endpoint of PFS will be summarised by Kaplan-Meier plots presented by treatment group. The median, upper quartile, lower quartile PFS and the proportion of patients who are progression-free at 3, 6, and 12 months will be presented along with 80% Wald CIs, obtained using the Brookmeyer-Crowley method (1982). Patients who have not progressed by the time of the data cut-off will be censored following the rules defined in Section 10.8.1.

The comparison between the treatment groups of PFS will be performed by fitting a Cox proportional hazard model (Cox 1975) with treatment group, HPV status (if there are at least 10 patients in each HPV status within each treatment group) and the interaction term between treatment and HPV status (if statistically significant at the 5% level). Efron's method (1977) will be used to handle tied events in any of the independent event intervals. The covariate-adjusted hazard ratio between the treatment groups, based on the profile partial likelihood from the fitted Cox proportional hazards model, will be presented as a measure of the treatment effect along with the respective 80% and 95% Wald CIs and the asymptotic p-value from the Wald test for the difference in the covariate-adjusted log hazards in the fitted model.

If the interaction term between treatment and HPV status is statistically significant, the hazard ratio would be presented separately for HPV+ and HPV- along with the p-value of the interaction term and the 95% Wald CI based on the profile partial likelihood estimate for the interaction effect. Additionally, a Kaplan-Meier plot will be presented by treatment group and HPV status if there are at least 10 patients in each HPV status within each treatment group.

The proportionality of hazards will be examined for the fitted Cox proportional hazards model for PFS using Log-minuslog plots and Schoenfeld residuals. If the proportional hazard assumption is violated between the treatment groups, a modified max combo (Roychoudhury et al 2021) using the Fleming and Harrington 1981 weights (Fleming & Harrington 1981) such as FH(0,0), FH(0.5,0.5), FH(0,0.5), FH(0.5,0) will be implemented for estimating the performance of the competing treatment groups for PFS. The p-value obtained from each of the modified max combo tests will be reported.

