6.1 Changes from Protocol

6.1.1 Major Changes

• Initial Data Cut-Off for Primary Analysis

Section 8.1 of the protocol states the *"initial data cut-off will occur approximately 9 weeks after completion of enrolment, when all patients are expected to have had at least 3 cycles of pembrolizumab, at least one post-treatment scan, and the opportunity for a post-treatment tumour biopsy."*. During the preparation of this SAP a decision was made to extend this to approximately 15 weeks after completion of enrolment, with the aim for patients to have at least two post-treatment scans. This is clarified in Section 12.5 of this SAP.

Inclusion of the HPV Stratification Factor in Modelling

Section 8.4.2 of the protocol states the fitted analysis of covariance (ANCOVA) model as the only method to analyse the primary efficacy endpoint and without reference to human papillomavirus (HPV) status as a possible covariate. HPV status has been used as the stratification factor in the design of the study and not accounting for this factor in the analysis model may enhance the unexplained variability in the fitted linear model. Therefore, the HPV status will be included as a covariate in the ANCOVA model, if there are at least 10 patients at each level within each treatment group.

The same approach has been taken for the analysis of the cancer-associated fibroblasts (CAFs), cluster of differentiation 8 (CD8⁺), tumour-infiltrating lymphocytes (TILs) and the programmed cell death ligand 1 (PD-L1) expressions.

The HPV stratification factor, as well as the possible treatment-covariate interaction, have also been added as predictors for the Cox proportional hazards model described in Section 10.8.1 of this SAP.

• Duration of Response (DoR)

As DoR is a time-to-event endpoint, it was decided that an analysis using the Kaplan Meier method would be more appropriate than the Confidence Interval (CI) approach for a binomial proportion. This is described in Section 12.5.4.2 of this SAP.

• Supportive Analyses

Section 8.4.5 of the protocol describes a competing risk approach, using Fine & Gray (1999) methods to further analyse PFS. It was decided during the preparation of this SAP to remove this analysis from the scope of this SAP.

• Primary Estimand

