8.1 Sample Size Considerations

An overall sample size of approximately 50 patients (25 per treatment group) is considered sufficient to assess the primary endpoint of the best percentage change in tumour size following treatment with setanaxib when administered with pembrolizumab, versus placebo when administered with pembrolizumab, in patients with recurrent or metastatic SCCHN. With 25 patients per treatment group, using a 2-sided t-test, there will be 85% power to detect a 20% mean difference between the treatment groups in best percentage change in tumour size, with an estimated SD of 30% and a 2-sided alpha of 20%. To mitigate risks from a higher than expected number of patients discontinuing the study early or declining to have imaging or biopsies at Week 9, up to an additional 20 patients (making a maximum of 70 patients) may be randomised.

The key secondary endpoints of numbers of CAFs, CD8⁺ TILs, and regulatory T-cells in tumour tissue and gene expression analysis in tumour tissue will be used to determine proof of concept. With 25 patients per treatment group, there will be 90% power to detect a limit fold change (LFC) of more than 1.5 in gene sequencing endpoints measured in tumour tissue, assuming at least 20 patients have an evaluable Baseline and post-Baseline tissue sample.

For the key secondary endpoint of PFS, if the true hazard ratio for PFS is 0.5, approximately 38 progression events as defined by RECIST v1.1 will be required to have > 80% power to demonstrate a statistically significant difference in PFS with 2-sided p<0.2.

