8.2 Randomisation

Randomisation will be performed via centralised interactive response technology (IRT). On Day 1, eligible patients will be assigned to setanaxib or placebo in a 1:1 ratio, stratified by HPV status. Each patient will receive a unique randomisation number when he/she is assigned treatment. Patients will be allocated to treatment according to the randomisation code.

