12.5.3.4 Sensitivity Analyses

In anticipation of small numbers of progression events within the subgroups of HPV status, a sensitivity analysis of the methods described in Section 12.5.3.1, will be repeated without HPV status.

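### A 5% interaction test decides whether the main PFS model yields one hazard ratio or two HPV-specific ones, so the single hazard ratio of the estimand and the power calculation is not secured as the main result

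*SAP*

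**What the plan says.** SAP 12.5.3.1 compares PFS between arms with a Cox model containing treatment, HPV status if each HPV level has at least 10 patients in each arm, and "the interaction term between treatment and HPV status (if statistically significant at the 5% level"). An adjusted treatment hazard ratio with 80% and 95% Wald intervals and a Wald p-value is to be taken from the fitted model. If the interaction is significant, "the hazard ratio would be presented separately for HPV+ and HPV"-negative patients, with the interaction p-value and a 95% interval for the interaction effect.

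SAP 6.1.1 lists this among the major changes from protocol: HPV status, "as well as the possible treatment-covariate interaction, have also been added as predictors" in the Cox model. Protocol 8.4.3 has treatment as the only covariate.

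Three other places bear on the point:
- SAP 9.1.2 gives the PFS summary measure as one hazard ratio between the two treatment groups.
- SAP 8.1 states that "if the true hazard ratio for PFS is 0.5, approximately 38 progression events as defined by RECIST v1.1 will be required" for more than 80% "power to demonstrate a statistically significant difference in PFS with 2-sided p<0.2".
- SAP 12.5.3.4 anticipates few progression events within HPV subgroups and plans that the PFS analysis "will be repeated without HPV status".

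**The concern.** The form of the main PFS result depends on a test made on the trial's own data. When the interaction is retained, a single adjusted treatment hazard ratio is no longer defined by the text. Under ordinary reference coding the treatment coefficient is the effect in the reference HPV level. The SAP names no reference level and gives no rule for averaging over strata.

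The analysis that then carries the main label no longer matches the estimand or the power statement, and the overall comparison remains only under a sensitivity label. Because HPV-specific hazard ratios appear only after a significant test, those that are reported will tend to overstate the difference between HPV groups. A chance finding could read as benefit in one HPV group and none in the other.

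**Working it through.** **Inputs.** From SAP 8.1 and 8.2: hazard ratio 0.5, about 38 events, two-sided alpha 0.20, 1:1 allocation, about 50 patients (up to 70). From SAP 12.5.3.1: interaction threshold 5%. Assumption, because the documents give no HPV prevalence: 30%, 40% or 50% of the events are HPV-positive.

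**1. The plan's own figure.** Schoenfeld's formula gives events = 4 × (1.2816 + 0.8416)² / (ln 0.5)² = 37.5, so 38. Power at 38 events = Φ(√38/2 × ln 2 − 1.2816) = Φ(0.855) = 80.4%. The figure reproduces, and it is for one overall hazard ratio.

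**2. What the interaction test needs.** With variance 4/events for each stratum's log hazard ratio, SE = √(4/e₁ + 4/e₂). Three quantities follow:
- Smallest ratio between stratum hazard ratios that reaches p<0.05: exp(1.96 × SE).
- Median ratio given that the rule fires with no true interaction: exp(2.2414 × SE), because 2.2414 is the value that |Z| exceeds with probability 0.025, half of the 5%.
- Chance of detecting a true two-fold difference: Φ(ln 2/SE − 1.96) + Φ(−ln 2/SE − 1.96).

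| HPV+ share | Events HPV+/HPV− | SE | Smallest significant ratio | Median ratio if fired, truth 1 | Detects two-fold |
|---|---|---|---|---|---|
| 30% | 11.4 / 26.6 | 0.708 | 4.0 | 4.9 | 16.5% |
| 40% | 15.2 / 22.8 | 0.662 | 3.7 | 4.4 | 18.2% |
| 50% | 19 / 19 | 0.649 | 3.6 | 4.3 | 18.7% |

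**3. What would be reported.** In 2,000,000 normal draws per scenario, with a true hazard ratio of 0.5 in both strata, the rule fires in 5% of trials. The median reported hazard ratios are then about 0.22–0.24 in one stratum and 1.07–1.13 in the other. With a true two-fold difference, the median reported ratio after firing is about 4.7–4.8 (40–50% HPV-positive). Direct simulation of Cox analyses (3,000 trials per scenario, 50 or 70 patients, 38 events) gave firing rates of 4.4–5.9% with no true interaction.

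**4. The 10-per-cell condition.** SAP 12.5.3.1 attaches it to the HPV main effect and does not say that it covers the interaction, though an interaction would normally need its main effect. Approximating the condition as at least 20 patients at each HPV level overall, the chance of meeting it is:
- 25 per arm: 8.5%, 55% and 88% at an HPV-positive prevalence of 30%, 40% and 50%.
- 35 per arm: 65%, 98% and 100%.

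If it does cover the interaction, the unconditional firing rate at 25 per arm with no true interaction is about 0.05 × 0.085 = 0.4%, 0.05 × 0.55 = 2.8% or 0.05 × 0.88 = 4.4%.

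**5. Information per stratum.** By the formula in step 1, power at a true hazard ratio of 0.5 is 46% and 69% (30:70 split of events), 53% and 65% (40:60), or 59% in each stratum (50:50). The SAP plans no stratum-level test, so these figures only show how little information each HPV-specific hazard ratio carries.

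**The case against.** The strongest reply is SAP 12.5.3.4. It repeats the PFS analysis without HPV status, with no trigger, and a treatment-only Cox model is the protocol's own PFS model. A reader might infer that the powered comparison is lost when the rule fires. It is not: the overall hazard ratio is produced in every trial, and what changes is its label. That stands. It does not settle which result is the main one, and it does not secure an HPV-adjusted overall hazard ratio.

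SAP 12.5.3.1 also never says that the overall hazard ratio is withheld. That is fair, but with the interaction in the model the text does not define one.

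Other stronger readings are tempting and are not supported:
- **That the switch is ad hoc.** The rule has a fixed threshold and is disclosed in SAP 6.1.1. The choice depends on the data, but it is pre-specified.
- **That it happens whenever p<0.05.** The 10-per-cell condition presumably applies as well, and at 25 per arm with low HPV-positive prevalence it would usually fail.
- **That the treatment effect is exaggerated.** What is exaggerated is the contrast between strata and the more extreme stratum hazard ratio, not the overall one.
- **That the false-positive rate rises.** It would be about 24% instead of 20% (two-sided) only if p<0.2 in either stratum counted as success. The SAP sets no such rule.

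Finally, PFS is a secondary endpoint in a proof-of-concept study and the rule fires rarely. This limits the consequence, but the ambiguity in the text remains.

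**Conclusion.** The point holds in a limited form. The main PFS model is chosen by a pre-test. When the interaction is retained, its treatment hazard ratio and p-value no longer correspond to the single hazard ratio of SAP 9.1.2 or to the one that 38 events power at 80.4%. The overall comparison is moved to a sensitivity analysis; it is not dropped.

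The problem is infrequent but misleading when it occurs: about 5% of trials with no true interaction and an eligible HPV term, fewer if the 10-per-cell condition fails, with a typical apparent difference between strata of more than four-fold. The test is also a weak guide to a real difference, since it misses a true two-fold one in more than 80% of trials. These sizes rest on the assumed 30–50% HPV-positive share of events and on the normal approximation, which the Cox simulations support for the firing rate.

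**What to change.** In SAP 12.5.3.1:
- State that the main PFS result is always the single overall hazard ratio from the model without the interaction (treatment, plus HPV status when the 10-per-cell condition is met), with 80% and 95% intervals and p-value.
- Remove the significance condition on the interaction. Fit the interaction in a separate exploratory model.
- When the 10-per-cell condition is met, report the interaction estimate, interval and p-value and both HPV-specific hazard ratios with intervals, whatever the interaction p-value, labelled as supplementary. The present text gives an interval for the interaction effect but does not clearly give one for each stratum.
- Say explicitly that the 10-per-cell condition governs the interaction as well as the main effect.

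SAP 6.1.1 should be aligned. SAP 12.5.3.4 can stay as it is. The change is best made before treatment codes are opened for the primary analysis.

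The cost is SAP wording; no new data or patients are needed. The small downside is that imprecise HPV-specific hazard ratios will be shown more often, so the exploratory label and the 10-per-cell condition matter.

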12.5.3.2 Change from Baseline in CAFs Level in Tumour Tissue

For the key secondary endpoint of CAFs level, (also referred to as smooth muscle actin [SMA]), it is hypothesised based on the mode of action of setanaxib that there will be a reduction in CAFs level. Data for patients with both baseline and postbaseline results, will be summarised using univariate statistics and will be graphically presented using both boxplots and spaghetti plots for each treatment group.

This secondary efficacy analysis will evaluate the effect of setanaxib on the ratio of postbaseline to baseline CAFs level using an ANCOVA model, including the same covariates as described for the primary analysis in Section 12.5.2.2. Zero values will be replaced as described in Section 12.5.2.1.

A summary of the qualitative CAFs level (in order of increasing severity: Negative, Low Positive, Moderate Positive, Strong Positive) will also be provided.

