Changes in tumour biomarkers will be correlated with change in tumour size and other efficacy parameters.

Safety Analysis:

The Safety Analysis Set will be used for the analysis of safety data (AEs, including AESIs, clinical laboratory tests, vital signs, 12-lead ECGs, and physical examination). The safety data will be presented descriptively and not formally analysed.

Protocol version and date: Version 4.0 (25 April 2023)

STUDY SCHEMATIC

Figure 1 Study Schematic

AE=adverse event; CAFs=cancer-associated fibroblasts; IV=intravenously; PFS=progression-free survival; PO=per os (orally, or via either a feeding tube or a percutaneous endoscopic gastrostomy device in case patients are unable to swallow tablets); q3w=every 3 weeks; R=randomisation; RECIST v1.1=response evaluation criteria in solid tumours version 1.1

* For patients with a suitable archival tumour biopsy sample available, the archival sample may be used to assess CAFs level and determine eligibility (Note: this can only be performed after the patient has provided signed informed consent). This will not dispense from the need for a recent pre-study tumour biopsy. ** Or earlier if progression occurs before 9 weeks.

SCHEDULE OF ASSESSMENTS

Table 1Schedule of Assessments

Study Period	Screening		Double-blind Treatment Period			Follo	w-up ^a
Study Weeks:	-5 to -1	BL	3, 6, 9, 12, 15, 18, 21, 24, 27, 30, 33, 36, 39, 42, 45, 48, 51, 54, 57, 60, 63, 66, 69, 72, 75, 78, 81, 84, 87, 90, 93, 96, 99, 102	105	ЕоТ	Last IMP	Refer to
Study Days (Visit Window):	-35 to -1	1	Every 21 days (±5)	735 (±3)	Visit	(±7 days)	'L'
Visit:	1	2	3 to 36	37	ЕоТ	Safety Follow-up	Efficacy Follow-up
Informed consent	Х						
Determination of eligibility ^b	Х	\mathbf{X}^{b}					
Randomisation		Х					
Demographics, ECOG performance status, and relevant medical history	Х	Х					
Height	Х						
Body weight	Х		Х	Х	Х	Х	
Body temperature	Х	Х	Х	Х	Х	Х	
Physical examination / symptoms- directed physical examination ^c	Х	Х	Х	х	Х	Х	
Pulse rate, SBP, and DBP	Х	Х	Х	Х	Х	Х	
12-lead ECG ^d	Х	Х	Х	Х	Х	Х	
Blood sampling:							
Pregnancy test (serum) ^e	Xe						
Haematology and biochemistry ^f	Х	Х	Х	Х	Х	Х	
Thyroid function test ^f		Х	Х	Х	Х	Х	

Study Period	Screening		Double-blind Treatment Period			Follow-up ^a	
Study Weeks:	-5 to -1	BL	3, 6, 9, 12, 15, 18, 21, 24, 27, 30, 33, 36, 39, 42, 45, 48, 51, 54, 57, 60, 63, 66, 69, 72, 75, 78, 81, 84, 87, 90, 93, 96, 99, 102	105	ЕоТ	Last IMP	Refer to

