6.0 Introduction

This SAP should be read in conjunction with the study protocol and electronic case report form (eCRF). This version of the SAP has been developed by ICON using protocol version v5.0 dated 12 December 2023 along with the local amendment for the United Kingdom (v4.2 dated 25 April 2023) and CRF v5.0 dated 19 September 2023. Any further changes to the protocol or eCRF that have an impact on the design or the planned statistical analysis will require updates to the SAP.

The initial version of the SAP will be signed prior to the biomarker interim analysis (see Section 11.0 for details). The final version of the SAP, will be issued for sponsor approval prior to the data cut off for the updated analysis (see Section 8.4 for details on the timing of database lock).

A separate Independent Data Monitoring Committee (IDMC) SAP (v1.0 dated 16 December 2022) documents the details of the regular safety and tolerability reviews performed by an unblinded IDMC.

The full set of tables, listings and figures (TLFs) described in this SAP will be produced for the primary analysis and the updated analysis. If there are patients continuing in the study after the updated analysis, a small set of adverse events (AEs), serious adverse events (SAEs) and other selected safety data listings will be updated and included in an addendum to the CSR. The full set of outputs will not be reproduced.

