12.0 Statistical Methods

With the exception of the unblinded statistician and programmers supporting the IDMC, all personnel involved with the analysis of the study will remain blinded until the initial database soft lock at the time of the primary analysis. Further details on the blinding and unblinding are given in the study Blinding Plan.

In this study, it is planned to recruit approximately 35 investigational centres in USA and Europe. Unless specified otherwise, data from all participating sites will be combined for the analysis, so that an adequate number of patients will be available for analysis. In the event that a single site enrols a large proportion of patients, a site effect may be explored as described in Section 12.5.5, otherwise no site effect will be assessed.

All table summaries will be presented by treatment group (including an overall group for safety tables) and by analysis visit where appropriate. Unscheduled visits will be windowed as described in Section 10.4. Unscheduled visit values will contribute to any assessment of worst/most severe results, but otherwise will only be displayed in listings. Additional details related to specific presentations are given in programming notes of the supporting TFL shells.

Categorical variables will be summarised descriptively using counts and percentages. Percentages will be rounded to one decimal place, except 100%, which will be displayed without any decimal places and percentages will not be displayed for zero counts.

Continuous variables will be summarised using univariate statistics, including the number of observations (n), mean, standard deviation, median, minimum and maximum. The minimum and maximum values will be displayed to the same level of precision as the raw data, the mean and median to a further decimal place and the standard deviation to two additional decimal places. In addition, for tumour and biomarker summaries, the geometric mean and the interval of (geometric mean +/- geometric standard deviation) may also be presented.

Analyses will be performed using SAS® (SAS Institute, Cary, NC, US) version 9.4 or higher.

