12.5.2.1 Imputation Methods

Imputation of missing target lesions will be performed using the scaling methods described in Section 10.7.3 and missing best percentage change from baseline will be imputed as described in Section 10.7.6.

Where analysis is performed on the ratio of postbaseline to baseline, zero values will be replaced with a constant equal to half of the smallest observed non-zero result across all patients (baseline and postbaseline).

No other imputation methods will be explored.

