12.5.2.2 Primary Analysis

The primary efficacy analysis will evaluate the effect of setanaxib on the best percentage change in tumour size using an ANCOVA model, including covariates for treatment, baseline tumour size and the randomisation stratification HPV status (if there are at least 10 subjects at each level within each treatment group).

The number of patients, unadjusted mean, and adjusted least squares (LS) means for each treatment group will be presented, together with the difference in adjusted LS means, 80% and 95% CIs and corresponding p-value from the fitted ANCOVA model.

A plot of the residuals against the fitted values will be produced to check the assumption of constant variance. Any systematic effect in this residual plot along will indicate that a suitable transformation (log transformation) should be applied on the response of the model as appropriate to stabilise the variability of the error.

A normal probability plot will also be plotted of the residuals of the fitted ANCOVA model in addition to a Shapiro-Wilk test, used to test for the distribution of normality of the residuals. If the normal probability plot shows a concave curve of the residuals against the normal quantiles along with the p-value obtained from the Shapiro-Wilk test being less than 0.05, then this indicates a violation of the ANCOVA model assumption of the errors being normally distributed.

If the ANCOVA model assumptions are not upheld, logarithmic transformations on the response will be applied to normalise the data. The log(post-baseline) to log(baseline) ratio will be analysed using an ANCOVA model, including covariates for treatment, log-transformed baseline tumour size and the randomisation stratification HPV status.

The number of patients, unadjusted geometric mean, and adjusted geometric LS means for each treatment group will be presented, together with the difference in adjusted geometric LS means, 80% and 95% CIs and corresponding p-value from the fitted ANCOVA model.

The validity of the assumptions of the fitted transformed model will be checked similarly.

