If the assumptions are not satisfied for the log-transformed model, a non-parametric method will be performed using a Ranked ANCOVA (Quade D. [1967]). A linear regression of the ranks of the best percentage change from baseline based on the ranks of the covariate for baseline tumour size and HPV status fitted as a class variable (ignoring treatment). The residuals from this regression model will then be analysed using an ANOVA model with treatment as the independent variable. The resulting p-value from the F test of this ANOVA will be reported.

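### The CAF, CD8+, FOXP3 and PD-L1 models adjust for baseline tumour size and leave out the marker's own baseline, probably through a cross-reference slip

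*SAP*

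**What the plan says.** For the primary endpoint, SAP 12.5.2.2 fits an ANCOVA "including covariates for treatment, baseline tumour size and the randomisation stratification HPV status", with HPV used only if there are at least 10 patients at each level within each arm. If the residual checks fail, the log refit is specified as "including covariates for treatment, log-transformed baseline tumour size and the randomisation stratification HPV status". The rank fallback regresses ranks "based on the ranks of the covariate for baseline tumour size and HPV status fitted as a class variable".

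For CAFs, SAP 12.5.3.2 models the effect "on the ratio of postbaseline to baseline CAFs level using an ANCOVA model, including the same covariates as described for the primary analysis", pointing to 12.5.2.2. SAP 12.5.3.3 (CD8+ TILs and FOXP3) and 12.5.4.4 (PD-L1) say only that the CAF analysis is repeated. No SAP section names a marker's own baseline as a covariate.

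Protocol v4.0, section 8.4.3, plans an ANCOVA for these markers that adjusts for differences at baseline, with a log transformation where appropriate. Section 8.4.4 covers the primary and secondary ANCOVAs. After failed residual checks it refits on the log response with log baseline as the covariate, and then falls back to a non-parametric method. SAP 6.1.1 lists one covariate change for CAFs, CD8+ TILs and PD-L1: the addition of HPV status. The SAP was written "using protocol version v5.0 dated 12 December 2023"; the protocol available here is v4.0 of 25 April 2023.

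**The concern.** In the primary analysis, baseline tumour size is the response's own baseline, so the covariate list is coherent. Carried over word for word to a tissue marker, the list loses that property. The model adjusts for a quantity with no stated link to the marker and omits the one baseline value most likely to predict the post-treatment value.

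CAFs, CD8+ TILs and regulatory T-cells are key secondary endpoints that protocol 8.3 and SAP 8.1 say will be used to determine proof of concept. They come from few paired biopsies. The power statement for the gene sequencing endpoints assumes at least 20 patients with evaluable pairs and does not say whether that is per arm. With so few pairs, precision lost to a missing covariate matters, and so does a chance difference between the arms at baseline.

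**Working it through.** **Figures in the plan.** There is no power or sample-size figure for the marker ANCOVAs to reproduce. The primary figure does reproduce: 25 per arm, difference 20, SD 30 and 2-sided alpha 0.20 give a noncentrality of 20/(30·√(2/25)) = 2.357 on 48 df and power of 85.4%, against the stated 85%. The 90% stated for gene sequencing cannot be checked, because no SD or alpha is given for it.

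**Tracing the covariates.** SAP 12.5.3.2 → 12.5.2.2 gives treatment, baseline tumour size and conditional HPV. SAP 12.5.3.3 and 12.5.4.4 → 12.5.3.2 give the same list. If the log refit and rank fallback of 12.5.2.2 also carry over, both name tumour size.

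**Assumptions for the illustration (none are in the documents).** Log scale; equal log-variance σ² before and after treatment; baseline/post correlation ρ of 0.2, 0.4 and 0.6; tumour size unrelated to the marker.

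**No eligibility cut on the marker.**
- Residual variance of log(post/baseline) without own baseline: 2σ²(1−ρ).
- With log baseline as covariate: σ²(1−ρ²).
- Ratio: 2/(1+ρ) = 1.67, 1.43, 1.25.
- CI width ratio: √(2/(1+ρ)) = 1.29, 1.20, 1.12, that is 29%, 20% and 12% wider.
- Equivalent size of 20 pairs per arm: 20·(1+ρ)/2 = 12, 14, 16.
- The cost shrinks as ρ rises: at ρ = 0.7 the width ratio is √(2/1.7) = 1.085.

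**Baseline range narrowed by an eligibility cut.** Let the log baseline be a normal truncated from below at c SD, with ρ the correlation before truncation. Its variance is vσ², where v = 1 + cλ − λ² and λ = φ(c)/(1−Φ(c)). The variance ratio becomes 1 + v(1−ρ)/(1+ρ), which equals 2/(1+ρ) when v = 1.

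| c (SD) | λ | v | CI width ratio, ρ = 0.2 | ρ = 0.4 | ρ = 0.6 |
|---|---|---|---|---|---|
| −1 | 0.288 | 0.630 | 1.19 | 1.13 | 1.08 |
| −0.5 | 0.509 | 0.486 | 1.15 | 1.10 | 1.06 |
| 0 | 0.798 | 0.363 | 1.11 | 1.08 | 1.04 |

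Simulation agrees to within 0.01 in every cell. The range is about 4% to 19% wider.

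**Where a cut applies.** Inclusion criterion 5 requires CAFs of at least 5%, but protocol 3.1 and 5.2.2 let suitable archival tissue meet it, with a separate recent biopsy supplying the analysed baseline. The narrowing is therefore direct only for patients who qualified on the baseline biopsy. PD-L1 may also be narrowed, through CPS ≥1 (criterion 7). CD8+ and FOXP3 have no cut.

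**Chance imbalance.** The log ratio fixes the slope of post on baseline at 1, whereas the true slope under these assumptions is ρ. A baseline difference d between arms on the log scale therefore shifts the estimate by −(1−ρ)d: 80%, 60% and 40% of d for ρ = 0.2, 0.4 and 0.6. Over repeated randomisations this averages to zero.

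**Type I error.** In simulation under the null at nominal 20%, rejection stayed between about 19% and 22% for the raw ratio with tumour size, the log ratio with tumour size and the log ratio with own baseline.

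**The case against.** **The ratio already uses baseline.** It does, but dividing by baseline fixes the adjustment instead of estimating it. On the log scale with equal variances the two coincide only when ρ = 1.

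**The plan departs from the protocol.** A reader might infer this. The documents do not show it: the SAP rests on protocol v5.0, which was not available. Even v4.0 does not say which baseline section 8.4.3 means; the marker's own is the natural reading. The SAP also sends presentation details to programming notes in the table shells, which might name the right covariate.

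**The response scale is unspecified.** A reader might infer this too, and it goes too far. SAP 10.1 defines the ratio as the plain quotient, and protocol 8.4.3 and 8.4.4 allow logging where appropriate or after failed residual checks. That is a conditional rule. Two features lean towards a log analysis: the zero rule, under which "zero values will be replaced with a constant equal to half of the smallest observed non-zero result across all patients", and the provision that "for tumour and biomarker summaries, the geometric mean and the interval of" geometric mean ± geometric SD may be shown. Fixing the log ratio in advance is a reasonable preference, but its absence is not an error in the plan.

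**The size is assumed.** This stands. The documents give no marker SD, correlation or effect size, and no alpha or decision threshold for these ANCOVAs. The figures illustrate the mechanism and do not estimate the loss in this trial. They also presuppose the log scale, whereas the response as first written is the plain ratio. A log-normal model may fit CAF percentages poorly, since they are bounded at 100%.

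**Conclusion.** The covariate point holds. As written, all four marker models adjust for baseline tumour size and none adjusts for the marker's own baseline. That this is a slip is an inference, supported by protocol v4.0 sections 8.4.3 and 8.4.4 and by the single covariate change declared for these markers in SAP 6.1.1.

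The consequence is a less precise estimate that is exposed to chance baseline imbalance. Under the stated assumptions, intervals are about 12% to 29% wider without an eligibility cut and about 4% to 19% wider where one narrows the baseline range. It would be wrong to conclude that the marker tests are invalid or biased on average, or that a powered proof-of-concept decision fails: type I error is unaffected, and the documents tie no numerical decision rule to these ANCOVAs. The point should be fixed because the markers carry the mechanism evidence and the correction is free. Confidence is high on what the text says and limited on the size.

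**What to change.** - In SAP 12.5.3.2, replace the cross-reference to the primary covariates with an explicit list: treatment; the baseline value of the same marker (logged when the response is logged, ranked in the rank fallback); and HPV status under the existing rule of at least 10 patients per level per arm.
- Carry this to 12.5.3.3 and 12.5.4.4, check it against protocol v5.0 and the table shells, and record it in 6.1.
- If tumour size was intended, say so in 6.1 and keep it only in addition to the marker's baseline.
- Optionally, state before the primary unblinding that the response is log(post-baseline/baseline), reported as geometric mean ratios.

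SAP 8.0 and 11.2 provide for an interim biomarker review by sponsor personnel outside the main study team who are unblinded to treatment. The change should therefore be made by people without access to that review, and its date recorded relative to it.

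The cost is SAP wording and the matching program change. Every patient with a paired sample already has the baseline value.
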